## II. **SPECIFIC AIMS** (Research Objectives)

We hypothesize that the administration of methergonovine will be associated with a 1 point greater reduction in uterine tone (on a 0-10 scale) at 10 minutes after administration compared to carboprost.

1. The primary outcome will be the uterine tone score on a 0 to 10 scale 10 minutes after administering the study drug. A score of 0 will mean the uterus has 'no tone'. A score of 10 will mean there is 'excellent tone'.
2. Secondary outcomes will include:
  - a) change in uterine tone from the time of study drug administration to 5 minutes later,
  - b) administration of an additional uterotonic agent after the first study drug
  - c) number of transfused blood products within 24 hours from the time of delivery,
  - d) any surgical intervention intended to control bleeding: i.e. Bakri balloon, O'Leary stitch, d&e, exploratory laparotomy, B-Lynch sutures, hysterectomy or interventional radiology artery embolization,
  - e) intraoperative quantitatively measured blood loss (QBL),
  - f) pre-delivery to postpartum change in serum hemoglobin,
  - g) vasopressor requirement or hypovolemic shock
  - h) postpartum admission to the intensive care unit (ICU),
  - i) need for postoperative mechanical ventilation,
  - j) nausea, vomiting, or diarrhea, abdominal pain, shortness of breath, headache, blurred vision, anxiety, chest pain, sweating, or palpitations within 2 hours postpartum
  - k) hypertensive emergency (SBP>/=160 or DBP>/=110)
  - l) EKG changes indicative of myocardial ischemia,
  - m) acute renal dysfunction,
  - n) length of postoperative hospital stay,
  - o) postpartum acute lung injury or circulatory fluid overload in the context of blood product transfusion,
  - p) allergic reaction deemed the result of blood product transfusion

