## III. **SUBJECT SELECTION**

### Inclusion Criteria/Exclusion Criteria:

Inclusion criteria will be all of the following: American Society of Anesthesiologists (ASA) I, II or III health status (minimal to no systemic disease), age between 18 and 50 yrs, and planned elective C/S or non-emergent C/S after labor, with suspected uterine atony at the time of delivery despite the administration of oxytocin.

Exclusion criteria for enrollment in the study will include any of the following: patients with essential hypertension or any hypertensive disorder of pregnancy, patients with cardiovascular disease, patients with active asthma (i.e. bronchodilator usage in the past 24 months), non-English speaking patients who are undergoing urgent, non-scheduled C/S, patients who refuse to accept blood transfusion (e.g. Jehovah's Witnesses), patients with a known coagulopathy or abnormal baseline coagulation profile, patients with known or suspected hypersensitivity to either of the two study drugs, and patients with known or suspected delayed PPH after leaving the operating room from the cesarean delivery.

Source of Subjects and Recruitment Methods:

Subjects will be recruited from women admitted to the labor & delivery (L&D) floor at the Brigham and Women's Hospital undergoing cesarean delivery who meet selection criteria as above.

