## VI. BIOSTATISTICAL ANALYSIS

- a. Specific data variables being collected for the study (e.g., data collection sheets).

Baseline patient characteristics will be collected and documented on data collection sheets. These characteristics will include:

1. patient MRN
2. randomization group
3. age
4. height, weight, BMI
5. gravidity and parity
6. baseline hematocrit and platelet count measured at the time of admission or on the day of delivery

- b. Statistical methods

The balance of patient characteristics between the two groups before intervention will be evaluated using standardized differences. Shapiro-Wilk test will be used to confirm whether the primary endpoint, uterine tone score 10 minutes after drug administration, satisfies the normality assumption. Multiple linear regression will be conducted when normality assumption satisfied. In the case when the normality assumption is not established, log transformation/box-cox transformation of the outcome will be carried out before modeling. For secondary endpoints that are dichotomous, logistic regression will be used to

examine the intervention effect after adjusting for potential confounders. For continuous secondary endpoints, such as intrapartum blood loss, we will evaluate its distribution before performing appropriate modeling. Trial site will be included as a covariate in all models to adjust for the stratification of randomization by hospital.

c. Power analysis (e.g., sample size, evaluable subjects, etc.)

Assuming a common within-group standard deviation in uterine tone score of 1.9 points, a minimum sample size of 41 randomized patients per group would provide 80% power at a two-sided alpha level of 0.05 to detect a 1.2 point difference in mean uterine tone score at 10 minutes post secondary uterotonic administration between groups using a two-sample t-test. A total of 50 patients per group (100 patients total) will need to be randomized to account for protocol violations. Since we currently perform 175 C/S monthly at BWH, and approximately 20 patients undergoing non-emergent C/S receive methergine or hemabate for uterine atony each month, we anticipate needing to enroll 1250 patients in total to be able to randomize 100 patients to receive the study intervention.

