## **VII. RISKS AND DISCOMFORTS**

Adverse reactions to methylergonovine include increased blood pressure, seizure, dizziness and headache, and nausea, vomiting, diarrhea and abdominal pain from uterine contractions. Rare effects include chest pain, myocardial infarction, coronary vasospasm, tachycardia, dyspnea, and hematuria. A large retrospective study of over 2 million parturients found no significantly increased risk of acute coronary syndrome or acute myocardial infarction after receiving methylergonovine. ACOG recommendations nonetheless state that methylergonovine should be avoided in patients with hypertension and cardiovascular disease.

The most common adverse reactions to carboprost include nausea, vomiting, diarrhea, as well as headache, myalgias, increased temperature and flushing. Due to its stimulation of smooth muscle contraction, modest increases in blood pressure may be seen, but these are generally clinically insignificant. Additionally, bronchospasm, abnormal ventilation-perfusion and hypoxia may occur, and may be particularly severe in patients susceptible to these complications. Carboprost is therefore contraindicated in patients with active asthma.

Patients with any contraindication to either of the study drugs will be excluded from participation in the study. Patients with a diagnosis of asthma will be interviewed to confirm if their asthma is active. Any patient who has used a bronchodilator within the past 24 months will be considered to have active asthma and will be excluded. If a patient carries a diagnosis of 'childhood asthma' and/or has not needed a bronchodilator for >24 months, they will be considered eligible to participate in the study. After enrollment, patients will be evaluated for all of the above side effects by a clinical investigator between at time of transfer to the postpartum floor and again between 18 to 24 hours after delivery. The obstetric 6-

week postpartum follow-up record will be reviewed by a clinical investigator to screen for thrombotic events or other side effects.

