## **ADVERSE REACTIONS**

The most common adverse reaction is hypertension associated in several cases with seizure and/or headache. Hypotension has also been reported. Abdominal pain (caused by uterine contractions), nausea and vomiting have occurred occasionally. Rarely observed reactions have included: acute myocardial infarction, transient chest pains, vasoconstriction, vasospasm, coronary arterial spasm, bradycardia, tachycardia, dyspnea, hematuria, thrombophlebitis, water intoxication, hallucinations, leg cramps, dizziness, tinnitus, nasal congestion, diarrhea, diaphoresis, palpitation, rash, and foul taste.

There have been rare isolated reports of anaphylaxis, without a proven causal relationship to the drug product.

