All continuous secondary outcomes were initially assessed for the normality of residuals from a multivariable linear regression model with trial site and baseline uterine tone as covariates. Outcomes displaying normally distributed model residuals were analyzed using multivariable linear regression, with effect size presented as adjusted difference in means with 95% CI. Outcomes with all non-zero values that displayed skewed linear regression model residuals were natural log-transformed and analyzed using multivariable linear regression, with effect size presented as adjusted ratio of geometric means with 95% CI. Outcomes containing at least one zero value that presented skewed linear regression model residuals were compared between groups using multivariable quantile regression, with effect size presented as adjusted difference in medians with 95% CI.

All binary outcomes were initially considered for comparison using multivariable logistic regression (for single measurements) or generalized estimating equations with a logit link (for repeated measurements) with trial site and baseline uterine tone as covariates. If the multivariable regression converged, effect size was presented as adjusted odds ratios with 95% CI. If the model did not converge due to low incidence, groups were compared using a Fisher's exact test and effect size presented as risk difference with exact 95% CI.

Time to receive second study drug was compared between groups using a multivariable Cox proportional hazards model, with effect size presented as adjusted hazard ratio with exact 95% CI. Complete-case analysis was performed for all secondary outcomes. All analyses were performed using SAS software version 9.4 (SAS Institute, Cary, NC).

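### Blood-pressure rise, a leading expected reaction to methylergonovine, has only a severe-range flag as a defined outcome; recording pre-drug and peak values for every woman would cheaply add a numeric comparison

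*Protocol*

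**What the plan says.** **Expected harm.** Detailed Protocol, Section VII: "Adverse reactions to methylergonovine include increased blood pressure, seizure, dizziness and headache". The Methergine package insert, Adverse Reactions: "The most common adverse reaction is hypertension associated in several cases with seizure and/or headache". Section VII describes carboprost's effect on pressure as modest and generally not clinically significant.

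**Outcome.** Section II lists, as secondary outcome (k), "hypertensive emergency (SBP>/=160 or DBP>/=110". The Protocol Summary repeats the name without a threshold inside its maternal-morbidity endpoint. The Secondary Endpoints list in Section V of the Detailed Protocol does not name it, and the SAP names no blood-pressure outcome.

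**Data capture.** The Data Collection Sheet has yes/no columns at SBP 160 or more and DBP 110 or more, and asks for the maximum only when the reading is above the cut. A reading of exactly 160 or 110 therefore sets the flag but asks for no value. The baseline list in Section VI ends with "baseline hematocrit and platelet count measured at the time of admission or on the day of delivery" and includes no blood pressure. No pre-drug blood pressure is visible on the data sheet, the intraoperative sheet or the interview guides.

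**Population.** Section III excludes "patients with essential hypertension or any hypertensive disorder of pregnancy, patients with cardiovascular disease".

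**Analysis.** SAP binary outcomes are modelled "with trial site and baseline uterine tone as covariates", with this fallback: "If the model did not converge due to low incidence, groups were compared using a Fisher's exact test".

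**The concern.** Blood pressure is one of the safety contrasts on which these two drugs are expected to differ. The plan turns it into an indicator at a severe-range cut, in women selected to have no hypertension. Most information about a moderate pressor effect lies below that cut and is not requested as a number.

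Without a pre-drug value, the change from before the drug cannot be estimated, nor can chance imbalance in starting pressure be adjusted for. Without a start time, outcome (k) does not say whether a high reading before the study drug counts.

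At stake is how informative the safety comparison is. The primary efficacy result is unaffected.

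**Working it through.** **1. The plan's own figures.** The plan states no power for blood pressure. Its sample sizes for uterine tone reproduce by the noncentral-t calculation (two-sided 0.05, 80% power):
- Protocol, 1.2 points with SD 1.9: 40.3, rounded up to 41 per group, as stated.
- SAP, 1 point with SD 1.5: 36.3, rounded up to 37, as stated.

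Both documents then plan 100 randomised women. I use 50 per arm.

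**2. Assumed inputs.** None of these comes from the documents:
- Peak SBP after the study drug is normal.
- Mean m in the carboprost (control) arm is 120 to 140 mmHg.
- Common SD is 12 to 18 mmHg.
- The methylergonovine mean is 10 mmHg higher.

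**3. Formulas.**
- Event probability: p = 1 − Φ((160 − m)/SD) for control and 1 − Φ((160 − m − 10)/SD) for methylergonovine.
- Fisher power: sum of the two binomial(50, p) probabilities over all tables with two-sided Fisher p ≤ 0.05.
- Continuous comparison: two-sample t-test, 98 df, noncentrality 10/(SD × √(2/50)). For SD 15 the standard error is 15 × 0.2 = 3.0 and the noncentrality 3.33, giving 91% power.

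**4. Results, 10 mmHg difference.**

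| Control mean | SD | P(SBP ≥ 160), control vs methylergonovine | Expected events out of 50 | Fisher power | t-test power |
|---|---|---|---|---|---|
| 120 | 12 | 0.04% vs 0.6% | 0.02 vs 0.3 | <0.1% | 98% |
| 120 | 15 | 0.4% vs 2.3% | 0.2 vs 1.1 | 0.1% | 91% |
| 120 | 18 | 1.3% vs 4.8% | 0.7 vs 2.4 | 1.7% | 79% |
| 130 | 12 | 0.6% vs 4.8% | 0.3 vs 2.4 | 2.3% | 98% |
| 130 | 15 | 2.3% vs 9.1% | 1.1 vs 4.6 | 13% | 91% |
| 130 | 18 | 4.8% vs 13.3% | 2.4 vs 6.7 | 18% | 79% |
| 140 | 12 | 4.8% vs 20.2% | 2.4 vs 10.1 | 54% | 98% |
| 140 | 15 | 9.1% vs 25.2% | 4.6 vs 12.6 | 48% | 91% |
| 140 | 18 | 13.3% vs 28.9% | 6.7 vs 14.5 | 40% | 79% |

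**5. Sensitivity.**
- 8 mmHg difference, same means and SDs: Fisher 0% to 30%, t-test 60% to 91%.
- Wider grid (SD up to 20, difference 8 to 15): Fisher 0% to 96%, continuous 51% to above 99%. The continuous comparison was ahead in every cell.
- Adjusting for the pre-drug value at an assumed correlation of 0.5 multiplies the SD by √(1 − 0.25) = 0.866. Power at 10 mmHg becomes 89% to above 99%.
- With no events in one arm, 5 of 50 in the other gives Fisher p = 0.056 and 6 of 50 gives p = 0.027.

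**6. What the calculation leaves out.** It models systolic pressure only. Outcome (k) also counts diastolic readings, so it would have somewhat more events and somewhat more power than shown.

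**The case against.** **A rise below the cut is not wholly lost.** A reader might infer that it would appear nowhere. The documents do not support that. Section VII says patients will be assessed for the side effects it lists, increased blood pressure among them. Section V makes study-medication side effects part of a secondary endpoint and has side effects from the medical record entered in REDCap. Section IX records all adverse events. This stands, and it limits the point: what is missing is a definition, a window, a number and a planned comparison. A large shift would also show partly as extra events under (k).

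**Absence from a broken table is weak evidence.** The data sheet is damaged by extraction, and the SAP uses variables (race, number of fetuses, birth weight) listed neither there nor in Section VI. Pre-drug pressures may well exist in the record. What can be said is that no document asks for them.

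**The SAP need not end at Fisher.** It goes there only if the logistic model fails to converge. In the central case (control mean 130, SD 15), both arms have at least one event with probability (1 − 0.9772^50) × (1 − 0.9088^50), about 68%. This also stands. Logistic regression adjusted for site and baseline tone would still not recover the values below the cut.

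**False reassurance.** A reader might infer that the trial would wrongly announce no difference in hypertension. That goes too far. The SAP reports an odds ratio or risk difference with a 95% CI, so sparse events would show as a wide interval, and the outcome is named as an emergency, not as hypertension in general.

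**A severe-range cut is a legitimate safety outcome.** Agreed; it should stay.

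**Conclusion.** The point holds as a cheap improvement. Outcome (k) is the only blood-pressure outcome with a definition. It lacks a start time and a pre-drug reference, and values are requested only above 160/110. Smaller rises have an undefined route into the side-effect and adverse-event data but no numeric comparison between arms.

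Under the stated assumptions, the threshold analysis has between almost no power and about even odds of detecting a 10 mmHg difference, where a continuous analysis would usually detect it. The direction was the same in every case tried. The size depends on the assumed control mean, and no document supports a 10 mmHg gap specifically, so the figures illustrate the loss and do not forecast it.

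The documents do not show that a pressor difference would go unreported or that a misleading conclusion would follow.

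**What to change.** 1. Keep (k) and its thresholds, but state that only readings from study-drug administration onward count. Align the data sheet so that a reading exactly at the cut also has its value recorded.
2. For every randomised woman, record the last SBP and DBP before the study drug, and the peak SBP and DBP in one fixed window after it. Use the same window in both arms, regardless of the alternate drug or the end of surgery. Sixty minutes is an example. The Methergine insert puts the mean peak level after intramuscular injection at 0.41 ± 0.21 h in healthy volunteers (0.41 × 60 = 25 minutes, SD 13). The Hemabate insert reports peaks at 15 to 60 minutes in five postpartum women.
3. Do not end the window at the alternate drug. Additional uterotonic use is itself secondary outcome (b), so stopping there would truncate on a post-randomisation outcome, make the windows unequal and sometimes end before peak drug level.
4. Analyse peak SBP and DBP by linear regression on arm, trial site and the pre-drug value. Report the adjusted difference in mmHg with 95% CI as a supportive safety outcome.
5. Add a sensitivity analysis that accounts for alternate-drug and vasopressor use.

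**Cost.** SAP and data-sheet wording, and four values for each of about 100 women (about 400 values) from the Epic record. Some dilution from the alternate drug and from vasopressors remains. The SAP is written in the past tense, so data collection may be complete. In that case, extract the values from the record and label the analysis post hoc.

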## III. **SUBJECT SELECTION**

### Inclusion Criteria/Exclusion Criteria:

Inclusion criteria will be all of the following: American Society of Anesthesiologists (ASA) I, II or III health status (minimal to no systemic disease), age between 18 and 50 yrs, and planned elective C/S or non-emergent C/S after labor, with suspected uterine atony at the time of delivery despite the administration of oxytocin.

Exclusion criteria for enrollment in the study will include any of the following: patients with essential hypertension or any hypertensive disorder of pregnancy, patients with cardiovascular disease, patients with active asthma (i.e. bronchodilator usage in the past 24 months), non-English speaking patients who are undergoing urgent, non-scheduled C/S, patients who refuse to accept blood transfusion (e.g. Jehovah's Witnesses), patients with a known coagulopathy or abnormal baseline coagulation profile, patients with known or suspected hypersensitivity to either of the two study drugs, and patients with known or suspected delayed PPH after leaving the operating room from the cesarean delivery.

Source of Subjects and Recruitment Methods:

Subjects will be recruited from women admitted to the labor & delivery (L&D) floor at the Brigham and Women's Hospital undergoing cesarean delivery who meet selection criteria as above.

#### **IV. SUBJECT ENROLLMENT**

Prior to admission, all participating obstetricians will provide their patients with the study Flier and consent form, which will be given to patients at their 28-week obstetric visit. This will allow potential subjects ample time to consider participation in the study. In addition, participating obstetricians will request consent from their patients to be contacted for research purposes, to provide a reminder of the study protocol closer to patients' delivery date. Those patients who agree to be contacted and are at 37 weeks gestational age or greater and eligible for the study (planning either vaginal or cesarean delivery) will be sent an email with the study's Flier and consent form attached from the research assistant. The email will be sent securely to protect patient confidentiality, in accordance with MGB Privacy and Security guidelines.

At the time of admission to the pre-operative area or labor and delivery unit, patients will be pre-screened for eligibility using the OB Pre-Screen questionnaire. The screening process will be documented in a Pre Screening Log without patient identifiers (patients will be logged using the first initial of their last name). All eligible patients undergoing planned elective C/S will be provided the Flier and consent form. A physician investigator (either the principal investigator or one of the co-investigators) who is not involved in the patient's care will review and discuss the study plan at this time, allowing subjects the opportunity to ask questions and address any of their concerns or any issues surrounding the study. Non-English speaking patients undergoing planned elective C/S will be interviewed with the assistance of an official in-person BWH medical interpreter. The consent will be verbally translated in full to their native language by the interpreter. Subjects interested in participating will then be consented by the principal investigator or physician co-investigator and enrolled in the study.

In the setting of the current COVID-19 pandemic, all study staff will wear appropriate PPE (as dictated by Partners-wide official policy) while working and during any conversation with study subjects. In addition, patients will only be approached in their room by a study physician to minimize personal contact, at which time they will discuss the study and obtain informed consent from those patients interested in participation. There will be attention to appropriate social distancing, hand hygiene and minimization of sharing any physical objects (e.g. pen, clipboard etc.) throughout the conversation with prospective study subjects. Should patients be interested in participation, written consent will be accepted.

Patients who are designated to have a C/S delivery after labor due to 'failure to progress' will be approached in a similar manner for consent at the time of decision for C/S. Non-English speaking patients undergoing unscheduled, urgent C/S will not be approached since translators may not be available in a timely fashion to assist with consent.

This study will only be conducted in women. Non-English speaking patients undergoing urgent C/S will not be approached since translators may not be available in a timely fashion to assist with consent. No other vulnerable populations will be specifically targeted, nor will any one group bear a disproportionate share of the burdens or benefits of the research.

A total of 1250 women will be enrolled, and 100 randomized in this study based on the power calculation included below and allowing for patient withdrawal or loss to followup; women will be assessed for eligibility and then randomized to either methylergonovine or carboprost groups with the aim of approximately 50 patients per group.

